#### 5.2.7.1.4 Adverse events of special interest

The term adverse events of special interest (AESI) relates to any specific AE that has been identified at the project level as being of particular concern for prospective safety monitoring and safety assessment within this trial, e.g., the potential for AEs based on knowledge from other compounds in the same class. AESIs need to be reported to the sponsor’s Pharmacovigilance Department within the same timeframe that applies to SAEs; see Section [5.2.7.2.2](#).

The following are considered as AESIs:

- Hepatic injury  
A hepatic injury is defined by the following alterations of hepatic laboratory parameters:
  - An elevation of AST (aspartate transaminase) and/or ALT (alanine transaminase)  $\geq 3$ -fold ULN combined with an elevation of total bilirubin  $\geq 2$ -fold ULN measured in the same blood sample, or
  - Aminotransferase (ALT, and/or AST) elevations  $\geq 10$  fold ULN

These lab findings constitute a hepatic injury alert and the subjects showing these lab abnormalities need to be followed up according to the 'DILI checklist' provided in the ISF. In case of clinical symptoms of hepatic injury (icterus, unexplained encephalopathy, unexplained coagulopathy, right upper quadrant abdominal pain, etc.) without lab results (ALT, AST, total bilirubin) available, the Investigator should make sure that these parameters are analysed, if necessary in an unscheduled blood test. Should the results meet the criteria of hepatic injury alert, the procedures described in the DILI checklist should be followed.

No further AESIs have been defined for this trial.

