#### 7.3.4 Safety analyses

Safety will be assessed as defined by the endpoints listed in Section [2.1.2](#) and [2.2.2](#) based on the treated set (TS). Safety analyses will be descriptive in nature and will be based on BI standards.

For all analyses the treatment actually administered (= treatment at onset) to the subject will be used (any deviations from the randomised treatment will be discussed in the minutes of the Report Planning Meeting).

Treatments will be compared in a descriptive way. The placebo group in the safety evaluation will consist of all subjects treated with placebo, regardless of the dose group in which they were treated. The test treatment groups will be compared to the placebo group in a descriptive way. Tabulations of frequencies/proportions will be used for the evaluation of categorical (qualitative) data, and tabulations of descriptive statistics will be used to analyse continuous (quantitative) data.

Measurements (such as ECGs, vital signs, or laboratory parameters) or AEs will be assigned to treatments (see Section [4.1](#)) based on the actual treatment at the planned time of the measurement or on the recorded time of AE onset (concept of treatment-emergent AEs). Therefore, measurements planned or AEs recorded prior to intake of trial medication will be assigned to the screening period, those between the trial medication intake and end of REP (see Section [1.2.6](#)) or next intake of study medication (BA/ FE part) will be assigned to the treatment period. Events occurring after the REP but prior to trial termination date will be assigned to 'follow-up'. These assignments including the corresponding time intervals will be defined in detail in the TSAP. Note that AEs occurring after the last per protocol contact but entered before database lock will be reported to Pharmacovigilance only and will not be captured in the trial database.

Additionally, further treatment intervals (called analysing treatments) may be defined in the TSAP in order to provide summary statistics for other than above periods, such as combined treatments, on-treatment totals, or periods without treatment effects (such as screening and post-study intervals).

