On treatment	BI tab fed, BI tab fasted, BI sol fasted	Date/time of administration of study drug of respective treatment period	Date/time of administration of study drug + REP (36 h) or date/time of administration of study drug in next period or 12:00 a.m. on day after last contact date (whichever occurs first)
Follow-up	F/U BI tab fed, F/U BI tab fasted, F/U BI sol fasted	Date/time of respective treatment administration of BI drug + REP (36 h)	Date/time of administration of study drug of next treatment period or 12:00 a.m. on day after last contact date

¹ See [Section 6.7](#) for definition of baseline, which will be used in the statistical analyses of safety laboratory data, ECG and vital signs.

AE summary tables will present results for the on-treatment phase only. All AEs will be listed.

In AE tables in CTR Section 15.3 (but not in Appendix 16.1.13.1.8.1 and Appendix 16.1.13.1.8.2 AE tables), the following total will be provided in addition:

SRD part:

- **"Total BI SRD"**, defined as the total over all on-treatment phases of the SRD part involving BI
- **"Total on-trt SRD"**, defined as the total over all on-treatment phases of the SRD part, including placebo

BA/FE part:

- **"Total BI BA/FE"**, defined as the total over all on-treatment phases of the BA/FE part involving BI

Safety laboratory data, ECG, qEEG, safety EEG, ERP, CADSS, [REDACTED] and vital signs will be analysed based on treatment groups (SRD part: Placebo, 0.25 mg BI, 0.75 mg BI, 2 mg BI, 5 mg BI, 10 mg BI, 20 mg BI, 30 mg BI) or on treatments in the respective treatment period (BA/FE part: BI tab fed, BI tab fasted or BI sol fasted) with clear differentiation between baseline (cf. [Section 6.7](#)) and post-baseline measurements. Follow-up laboratory measurements will be listed, but will not be used in descriptive summaries.

More details on the technical implementation of these analyses are provided in the ADS Plan of this TSAP.

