6.7 BASELINE, TIME WINDOWS AND CALCULATED VISITS

In all analyses (except for analyses of PD endpoints and analyses of ECG variables), the last available off-treatment value determined prior to the dosing of the respective study drug will be defined as baseline. This means that a separate baseline is defined for each study treatment of the BA/FE part. Off-treatment in this context means that a value measured within an on-treatment phase, as defined in [Table 6.1: 2](#), will not be used as baseline for any study treatment.

Table 6.7: 1 Baseline for [REDACTED] and ERP endpoints

Post-baseline value		Corresponding baseline value	
Planned time	Clock time	Planned time	Clock time
4:00	12:00	-20:00	12:00
24:00	08:00	-24:00	8:00
48:00	08:00	-24:00	8:00
72:00	08:00	-24:00	8:00

Table 6.7: 2 Baseline for qEEG endpoints

Post-baseline value		Corresponding baseline value	
Planned time	Clock time	Planned time	Clock time
0:45	08:45	-23:00	09:00
1:15	09:15	-23:00	09:00
3:00	11:00	-21:00	11:00
8:00	16:00	-16:00	16:00
24:00	08:00	-23:00	09:00
48:00	08:00	-23:00	09:00
72:00	08:00	-23:00	09:00

Table 6.7: 3 Baseline for additional analysis of qEEG endpoints, using first value after drug administration as baseline

Post-baseline value		Corresponding baseline value	
Planned time	Clock time	Planned time	Clock time
1:15	09:15	0:45	08:45
3:00	11:00	0:45	08:45

A centralised evaluation of 12-lead ECG recordings is performed at the time points specified in [Table 6.7: 4](#) for the SRD part and in [Table 6.7: 5](#) for the BA/FE part.

Table 6.7: 4 Time schedule of 12-lead ECG recordings with centralised evaluation (SRD part)

Visit	Day	Planned time [hh:mm] - relative to first drug administration	Study phase
2	-1	-25:00	Baseline
	1	00:30	On-treatment
		01:10	
		01:30	
		02:00	
		03:00	
		04:00	
		06:00	
		08:00	
		12:00	
	2	24:00	
		34:00	
	3	48:00	Follow-up
	4	72:00	

Table 6.7: 5 Time schedule of 12-lead ECG recordings with centralised evaluation (BA/FE part)

Visit	Day	Planned time [hh:mm] - relative to first drug administration	Study phase
2/3/4	-1	-25:00	Baseline
	1	00:30	On-treatment
		01:05	
		02:00	
		04:00	
		08:00	
	2	24:00	Follow-up
	3	48:00	
	4	72:00	

Three triplicate ECGs will be recorded as the baseline before the first drug administration within each treatment period. Within each triplicate, the mean of ECG variables will be calculated. The mean over the three triplicates will be used as baseline for ECG variables.

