7.8.2 Laboratory data

The analyses of laboratory data will be descriptive in nature and will be based on BI standards "Handling, Display and Analysis of Laboratory Data" (9).

Analyses will be based on normalised values, which means transforming to a standard unit and a standard reference range. The original values will be analysed if the transformation into standard unit is not possible for a parameter.

Descriptive statistics of baseline and on-treatment laboratory values over time and for the difference from baseline (see [Section 6.7](#)) will be provided. Frequency tables of changes between baseline and last value on treatment with respect to the reference range will be presented.

Unscheduled measurements of laboratory data will be assumed to be repeat measurements of the most recent scheduled measurement (e.g. for follow-up or confirmation of a particular value). Therefore, unscheduled measurements will be assigned to the planned time point of the previous scheduled measurement. Descriptive statistics will be calculated by planned time point based on the worst value of the subject at that planned time point (or assigned to that planned time point).

Laboratory data will be compared to their reference ranges. Values outside the reference range as well as possibly clinically significant values will be highlighted in the listings.

Clinically significant abnormal laboratory values are only those identified either in the Investigator's comments or at the Report Planning Meeting at the latest. It is the Investigator's responsibility to decide whether a lab value is clinically significant abnormal or not. Standard or project-specific rules for flagging clinically significant values in an automated manner will

not be applied in this study. Clinically relevant findings in laboratory data will be reported as baseline conditions (prior to first administration of study treatment) or as AEs (after first administration of study treatment) if judged clinically relevant by the investigator, and will be analyzed as such.

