7.8.3 Vital signs

The analyses of vital signs (blood pressure, pulse rate, respiratory rate, body temperature) will be descriptive in nature. Descriptive statistics of vital signs over time and for the difference from baseline (see [Section 6.7](#)) will be provided.

Unscheduled measurements of vital signs will be assigned to planned time points in the same way as described above for laboratory data. However, for vital signs, descriptive statistics will be calculated by planned time point based on the last value of the subject at that planned time point (or assigned to that planned time point). If the time of measurement is missing for a scheduled post-baseline measurement, the scheduled measurement will be used in calculation of descriptive statistics (as time difference between scheduled and unscheduled cannot be assessed).

If the time of measurement is missing for an unscheduled measurement, this measurement will be listed but will be ignored for the calculation of descriptive statistics.

Clinically relevant findings in vital signs data will be reported as baseline conditions (prior to first administration of study treatment) or as AEs (after first administration of study treatment) if judged clinically relevant by the investigator, and will be analyzed as such.

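### Unscheduled laboratory and vital-sign values are carried back to the previous planned time without a stop at dosing, so early post-dose values can miss the post-dose summary rows

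*SAP*

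**What the plan says.** SAP 7.8.2 treats an unscheduled laboratory value as a repeat of the most recent scheduled one, so that "unscheduled measurements will be assigned to the planned time point of the previous scheduled measurement". The summary then takes the worst value in each slot: "Descriptive statistics will be calculated by planned time point based on the worst value of the subject at that planned time point".

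SAP 7.8.3 carries the rule over: "Unscheduled measurements of vital signs will be assigned to planned time points in the same way as described above for laboratory data". Here the last value in the slot is used. There is one exception: for an unscheduled vital sign without a recorded time, "this measurement will be listed but will be ignored for the calculation of descriptive statistics".

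Protocol 7.3.4 assigns measurements to treatment "based on the actual treatment at the planned time of the measurement", sends those planned before intake to screening, and leaves the detail to the SAP.

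Other parts of the SAP work by actual time. Tables 6.1: 1 and 6.1: 2, whose titles also cover laboratory data and vital signs, start each on-treatment phase at the actual date/time of administration and end it no later than 36 h afterwards. Section 6.1 promises analysis "with clear differentiation between baseline" and post-baseline values, and says that follow-up laboratory values are listed but not summarised. In Section 6.7, "the last available off-treatment value determined prior to the dosing of the respective study drug will be defined as baseline", and a value measured during an on-treatment phase cannot serve as baseline.

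**The concern.** An unscheduled value taken after the dose but before the first planned post-dose assessment has two conflicting labels. By planned time it is pre-dose. By actual time it is on treatment. The SAP does not say which label decides the row of the over-time table.

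The repeat-measurement premise does not fit every unscheduled sample either. For clinical signs of liver injury without available results, protocol 5.2.7.1.4 asks for liver tests "if necessary in an unscheduled blood test". That passage does not say which row the result belongs in, but it shows that some unscheduled samples are prompted by an event.

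What is at stake is the descriptive picture of the first hours after dosing in a first-in-human trial. Predicted time of peak concentration is 1.39 h (protocol Table 1.2.5: 1), inside the 0 to 4 h laboratory gap. The SAP took more care with ECGs: 7.8.4 excludes unscheduled recordings, and also pre-dose recordings actually made after the first dose. Laboratory data and vital signs have no such condition.

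**Working it through.** The plan gives no figure to reproduce. The check applies the carry-back rule to the planned times in the two flow charts.

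**Inputs**
- SRD laboratory panels: -72:00, 4:00, 24:00 and 72:00. The Day -2 entry is only a drug screen and breath test.
- BA/FE laboratory panels: -72:00 once, before the first period, then 4:00, 24:00 and 72:00 after each dose. The later periods have no pre-dose panel of their own.
- Vital signs: -25:00, then 0:15 as the first post-dose time (SRD) or 0:30 (BA/FE). The -25:00 reading is taken in every BA/FE period.
- BA/FE doses at least 5 days (120 h) apart; residual effect period 36 h.

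**Slot inherited by an unscheduled post-dose value**

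| Data | Taken after dosing | Slot inherited |
|---|---|---|
| SRD laboratory | 0 to 4 h | -72:00 |
| BA/FE laboratory, period 1 | 0 to 4 h | -72:00 |
| BA/FE laboratory, periods 2 and 3 | 0 to 4 h | 72:00 of the preceding treatment |
| SRD vital signs | 0 to 0:15 | -25:00 |
| BA/FE vital signs | 0 to 0:30 | -25:00 of the same period |

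For BA/FE periods 2 and 3, the inherited slot lies at 72 - 120 = -48 h relative to the new dose when the interval is the minimum. Because 72 h > 36 h, it falls in the preceding treatment's follow-up phase. If follow-up in SAP 6.1 means that phase, the value is listed and not summarised. This slot applies in 12 × 2 = 24 of the 36 planned subject-periods.

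**What 6.7 protects.** The value was measured on treatment, so it cannot be the baseline. But 6.7 does not move it to the 4:00 row. Whether a program puts it in the pre-dose row or drops it, it is missing from the post-dose rows.

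**Illustration (assumed values, high values being worse).** Six subjects are at 100 throughout, except that one reads 1000 in an unscheduled sample at 2 h and is back at 100 at 4 h.
- As written, 4:00 row: mean 100; change from baseline 100 - 100 = 0.
- Assigned to 4:00 with the worst value: mean (5 × 100 + 1000)/6 = 250; change 250 - 100 = +150.
- As written, Day -3 row: 100 or 250, depending on whether planned time overrides 6.1 and 6.7. The baseline stays at 100 in either case.

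**Late direction.** An unscheduled laboratory value after 36 h and before 72:00 is follow-up by actual time and so is not summarised under 6.1. Under 7.8.2 it is assigned to 24:00, where the worst value is summarised. The two sections disagree.

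**The case against.** The strongest reply is that the SAP does set limits at dosing. Sections 6.1 and 6.7 work by actual time, and protocol 7.3.4 defers to the SAP, so a careful programmer would put the value in the new treatment's phase. That stands as far as baseline is concerned. It does not settle the table row, because 7.8.2 and 7.8.3 are also SAP text and state the opposite rule without an exception for dosing.

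Three stronger readings are tempting, and the documents do not support them.
- A reader might infer that an acute rise could appear as a fall from baseline. Section 6.7 rules this out: the misplaced value cannot be the baseline.
- A reader might infer that in the crossover the value is summarised under the wrong formulation or food state. For laboratory data the inherited slot is in follow-up, so the value leaves the summaries. Vital signs stay within their own period.
- A reader might add the early and late laboratory windows, 4 + 36 = 40 of 72 h (56%), and take that as the share of values hidden. Of those 40 hours, 36 are in the late direction, where the worst-value rule keeps an abnormality visible at 24:00. Values are lost from the post-dose rows in 4 of 72 h (5.6%), and these are clock hours, not probabilities.

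The impact is also limited. All individual values are listed, out-of-range laboratory values are highlighted, and clinically relevant findings are reported as adverse events. The SRD primary endpoint rests on drug-related adverse events, which are assigned by onset. Finally, the laboratory standard cited as SAP reference 9 and the ADS Plan are not available here, and either may contain the missing condition.

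**Conclusion.** The point holds as a conflict within the SAP. Planned-time carry-back (7.8.2 and 7.8.3, in line with protocol 7.3.4) meets actual-time phases and baseline (6.1 and 6.7), with no stated precedence. As written, timed unscheduled values are kept out of the post-dose rows if taken in the first 4 h for laboratory data, the first 15 min for SRD vital signs or the first 30 min for BA/FE vital signs. They could also enter a pre-dose row. The late laboratory inconsistency is secondary.

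The effect is confined to descriptive safety tables and depends on such samples being taken; the documents do not give their number. The conclusion assumes that the unseen standard and ADS Plan add no dosing condition. For the BA/FE laboratory case it also assumes that follow-up means the phase after 36 h. The change is worth making because the affected laboratory window contains predicted peak exposure and the correction is small.

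**What to change.** Add to SAP 7.8.2 and 7.8.3: *Unscheduled values are not carried back across a drug administration; treatment and phase follow the actual date/time of measurement (Tables 6.1: 1 and 6.1: 2). A post-dose value taken before the first planned post-dose time is assigned to that first post-dose time of the same period, using the worst value for laboratory data. For vital signs, such early values are kept out of the pre-dose row and listed as post-dose.*

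Vital signs need the separate clause because, under the last-value rule, the scheduled 0:15 or 0:30 reading would supersede an early value moved into that slot.

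State as well how 6.1 and 7.8.2 are reconciled for unscheduled laboratory values after 36 h and before 72:00. If phase follows actual time, repeats of an abnormal 24 h result taken after 36 h leave the summary and appear only in listings, so this should be a deliberate choice.

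The cost is these few sentences and a date/time condition in the analysis dataset program. No new data are needed.

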7.8.3 Vital signs

The analyses of vital signs (blood pressure, pulse rate, respiratory rate, body temperature) will be descriptive in nature. Descriptive statistics of vital signs over time and for the difference from baseline (see [Section 6.7](#)) will be provided.

Unscheduled measurements of vital signs will be assigned to planned time points in the same way as described above for laboratory data. However, for vital signs, descriptive statistics will be calculated by planned time point based on the last value of the subject at that planned time point (or assigned to that planned time point). If the time of measurement is missing for a scheduled post-baseline measurement, the scheduled measurement will be used in calculation of descriptive statistics (as time difference between scheduled and unscheduled cannot be assessed).

If the time of measurement is missing for an unscheduled measurement, this measurement will be listed but will be ignored for the calculation of descriptive statistics.

Clinically relevant findings in vital signs data will be reported as baseline conditions (prior to first administration of study treatment) or as AEs (after first administration of study treatment) if judged clinically relevant by the investigator, and will be analyzed as such.

7.8.4 ECG

Abnormal findings will be reported as baseline conditions (prior to first study drug administration) or as AEs (from first study drug administration onwards) if judged clinically relevant by the investigator.

Descriptive analysis of ECG endpoints will be based on the TS.

ECG measurements will not be included in the statistical analysis if one of the following applies:

- No date or time available for ECG measurement
- Pre-dose measurement done after first drug administration
- On-treatment measurement done before first drug administration
- Measurement is a repeated measurement
- More than 3 single ECGs (i.e., measurements from 4th single ECG onwards will not be included)
- Unscheduled measurements

Listing of individual data

For all quantitative endpoints, listings of individual data will be shown in Appendix 16.2. Occurrences of notable findings will be flagged.

Categorical endpoints

For the categorical endpoints, frequency tables will be provided.

For all subjects with any notable finding in quantitative ECG recordings, a separate listing will be created as end-of-text display (based on the same display template as in Appendix 16.2), and the corresponding time profiles of QTcF, QT, HR, PR and QRS will be presented in figures.

Quantitative endpoints

Descriptive statistics (N, mean, SD, min, median, max) will be provided for the absolute values and changes from baseline over time of QTcF, HR, QT, PR and QRS. The time profiles of mean and SD for the changes from baseline on treatment will be displayed graphically by treatment.

Absolute values and changes from baseline (per time point) of QTcB and RR will only be listed, i.e., no statistical summaries will be provided for these quantitative endpoints.

Appropriateness of heart rate correction methods of QT interval

To evaluate the appropriateness of the heart rate correction methods, the slope of the relationship of QTcF interval versus RR interval will be estimated separately for off-drug values and active treatment, by applying the random coefficient model described in [Section 10.2](#) using the QTcF and RR variable values per time point. A scatterplot of QTcF vs RR including the overall regression lines will be included in the Statistical Appendix of the CTR. The resulting (fixed effect) slope together with two-sided 95% confidence intervals will be included in the footnote for this plot.

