#### Stopping Rules Related to Dose Groups:

- In case of any safety concerns, as listed below but not limited to them, the trial will be mandatorily discontinued. Occurrence of severe non-serious adverse events

considered as drug-related by the investigator in 2 subjects of the same dose group (8 subjects) in the SRD-Part, or 3 subjects of the BA/ FE group (12 subjects), or occurrence of at least one drug-related serious adverse event (SAE). Moreover, dose escalation in the SRD-Part will be terminated, if more than 3 of the actively dosed subjects at one dose level show drug-related and clinically relevant adverse events of at least moderate intensity.

- Clinical apparent seizures/ convulsions in one or more subjects in the same dose group.
- EEG changes consistent with pro-convulsive activities (e.g., spike and wave) that is considered to be drug-related in two or more subjects of the same dose group.
- Clinically relevant changes in the neurological assessment indicating dose-limiting intolerance that is considered to be drug-related in one or more subjects of the same dose group.
- Dose escalation in the SRD-Part or treatment in the BA/ FE-Part will be stopped, if at least 2 subjects on active treatment at one dose level (SRD-Part) or 2 subjects in the BA/ FE-Part have relevant individual QT prolongations, i.e., a QTc increase of greater than 60 ms from baseline and/ or an absolute QT or QTc greater than 500 ms, as confirmed by a repeat ECG recording.
- Dose escalation in the SRD-Part will be stopped, if the  $C_{\max}$  or  $AUC_{0-24h}$  of at least 1 subject of one dose group increases above the following exposure thresholds or if the estimated geometric mean exposure is expected to exceed a  $C_{\max}$  of 1560 nM or an  $AUC_{0-24h}$  of 2490 nM\*h. In this case, one or two additional dose levels lower than the planned next dose level may be given, as long as the expected geometric mean exposure values of the interim dose do not exceed these exposure thresholds. Estimation will be done based on preliminary pharmacokinetic results of preceding dose groups (see Section [7.4](#))

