## 5.2.4 Electrocardiogram (SRD-Part)

### 5.2.4.1 12-lead resting ECG

#### Recording

Twelve-lead resting ECGs (I, II, III, aVR, aVL, aVF, V1 - V6) will be recorded using a computerised electrocardiograph (e.g., MAC VU360, [REDACTED]) at the time points given in the [Flow Chart](#). Electrode placement will be performed according to the method of Wilson, Goldberger and Einthoven.

To achieve a stable heart rate at rest and to assure high quality recordings, the site personnel will be instructed to assure a relaxed and quiet environment, so that all subjects are at complete rest.

All ECGs will be recorded for a 10 second duration after subjects have rested for at least 5 minutes in a supine position. ECG recording will always precede all other study procedures scheduled for the same time (except for blood drawing from an intravenous cannula that is already in place) to avoid compromising ECG quality.

ECGs will be recorded as single and triplicate ECGs, as indicated in the [Flow Chart](#).

ECGs may be repeated for quality reasons, for instance due to alternating current artefacts, muscle movements, or electrode dislocation. The repeat ECGs are assigned to the respective scheduled time point. Additional (unscheduled) ECGs may be recorded for safety reasons.

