5.3 FURTHER ENDPOINTS

5.3.1 Safety parameters

Safety and tolerability of BI 1569912 will be assessed based on further safety parameters defined in **Section 2.2.2.1 of the CTP**:

- *AEs (including clinically relevant findings from the physical examination)*
- *Safety laboratory tests*
- *12-lead ECG*
- *Continuous ECG monitoring (SRD-Part, only)*
- *Vital signs (blood pressure, pulse rate, respiratory rate, body temperature)*
- *Columbia-Suicide Severity Rating Scale (C-SSRS)*
- *Standardized physical/ neurological assessment [only as part of AE analysis]*
- *Assessment of dissociative symptoms ([...] CADSS)*
- *Electroencephalogram (EEG) [i.e., safety EEG, abnormal or normal]*

CADSS

CTP: *The CADSS is a clinician administered measure of perceptual, behavioural and attentional alterations during active dissociative experiences. The scale contains 23 subjective items, each rated from 0 (not at all) to 4 (extremely).*

The total score of the CADSS is the sum of the 23 item scores, ranging from 0 to 92. Statistical analysis of the CADSS will be based on the total score.

12-lead ECG endpoints

For the definition of baseline and a summary of time points please refer to [Section 6.7](#).

Quantitative ECG endpoints:

The following quantitative ECG endpoints will be determined for the ECG variables QTcF, QT, HR, PR, QRS, RR and QTcB derived as described in [Section 10.1](#):

- absolute values (per time point)
- changes from baseline (per time point)
- percent changes from baseline (per time point; for HR, PR, QRS)

Categorical ECG endpoints

[figure not shown]
The following categorical ECG endpoints will be determined based on the quantitative ECG endpoints.

[figure not shown]
- New onset (meaning that this or a higher category was not present at baseline) of maximum QTcF interval > 450 to 480 msec, > 480 to 500 msec, or > 500 msec on treatment. For assignment of a particular subject to one of the above categories, all time points on-treatment (refer to [Table 6.7: 4](#) and [Table 6.7: 5](#)) will be considered.
- Maximum change from baseline in QT interval of ≤ 60 msec, or > 60 msec on treatment
- Maximum change from baseline in QTcF interval of ≤ 30 msec, > 30 to ≤ 60 msec, or > 60 msec on treatment

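### The SAP labels the BA/FE 24 h ECG as follow-up although it lies inside the 36 h on-treatment window, and its exclusion rule drops ECGs repeated for quality

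*SAP*

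**What the plan says.** **On-treatment window.** SAP 6.1, Table 6.1:2, ends the BA/FE on-treatment phase at "Date/time of administration of study drug + REP (36 h) or date/time of administration of study drug in next period", or shortly after last contact, whichever comes first. The table's title mentions AEs, laboratory data and vital signs but not ECGs. Protocol 7.3.4, however, names ECGs among the measurements assigned to treatment from dosing to the end of the residual effect period (REP).

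**ECG phase tables.** SAP 6.7 gives each part its own schedule:
- Table 6.7:4 (SRD): on-treatment from 0:30 to 34:00, follow-up at 48:00 and 72:00.
- Table 6.7:5 (BA/FE): on-treatment from 0:30 to 8:00, follow-up at 24:00, 48:00 and 72:00.

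**How the labels are used.** For the new-onset QTcF categories, SAP 5.3.1 says: "For assignment of a particular subject to one of the above categories, all time points on-treatment" are considered, and it points to these two tables. The maximum-change categories for QT and QTcF are also defined on treatment.

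**Repeats.** SAP 7.8.4 lists grounds for leaving an ECG out of the statistical analysis. One is "Measurement is a repeated measurement". Unscheduled measurements are a separate ground, so a repeat must mean something else. Protocol 5.2.4.1 and 5.2.5 allow a repeat when a tracing is spoiled by electrical interference, movement or a displaced electrode, and state: "The repeat ECGs are assigned to the respective scheduled time point".

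**The concern.** The categorical endpoints record each subject's worst value on treatment, so they depend entirely on which tracings are admitted. Two rules affect admission.

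First, the same clock time after dosing is on-treatment in one part of the trial and follow-up in the other, and no reason is given. A QTcF rise seen only at 24 h would be counted in an SRD subject but not in a BA/FE subject.

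Second, a tracing repeated because the first attempt was technically poor is the one that should represent the time point. The protocol files it there; the SAP removes it.

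These tables carry some weight. Amendment 7 added triplicate ECGs in the SRD part to help justify a waiver of a dedicated thorough QT study, and SAP section 4 then dropped the planned concentration–ECG analysis. That leaves the descriptive and categorical ECG output as the main QT evidence from this trial.

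**Working it through.** **1. Phase labels against the REP.** Call an ECG on-treatment if its planned time is no later than the REP, otherwise follow-up. Use 36 h (SAP 6.1) and, as a variant, the roughly 15 h that protocol 1.2.7 derives from half-life before settling on up to 36 h.

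| Table | Post-dose times | Mislabelled at 36 h | Mislabelled at 15 h |
|---|---|---|---|
| 6.7:4 (SRD) | 13 | 0 | 2 (24:00, 34:00) |
| 6.7:5 (BA/FE) | 8 | 1 (24:00) | 0 |

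The SRD labels need a cut-off of at least 34 h and below 48 h. The BA/FE labels need one of at least 8 h and below 24 h. These ranges do not overlap, so no single window produces both tables.

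**2. Could the next dose end the BA/FE window early?** No. The wash-out is at least 5 days, and 5 × 24 = 120 h, well beyond 36 h.

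**3. Size.** BA/FE ECG times within 36 h: 0:30, 1:05, 2:00, 4:00, 8:00 and 24:00, so 6. Table 6.7:5 counts 5. With 12 planned subjects and 3 periods:
- As labelled: 12 × 3 × 5 = 180 subject-time points.
- With 24:00 included: 12 × 3 × 6 = 216.
- Left out: 216 − 180 = 36, and 36/216 = 16.7%.

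**4. What happens to a quality repeat.** Under SAP 7.8.4 the repeat is out. The public text does not say what becomes of the tracing it replaced, so there are two branches:
- *The poor tracing stays in.* An artefact can then set a worst-case category.
- *The poor tracing is treated as missing.* SAP 6.6 then averages the remaining one or two replicates. Where only one ECG per time point is analysed, none remains and the time point is empty. That applies to post-dose BA/FE ECGs, which carry no triplicate footnote in the flow chart, and to the 30 mg group, where protocol 5.2.4.1 sends only the first replicate for central evaluation.

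In both branches a valid tracing is lost. The documents give no rate of quality repeats, so the number affected cannot be estimated.

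**The case against.** **On the phase label.** Table 6.1:2 does not mention ECGs in its title, the pharmacokinetic argument alone gives an REP of about 15 h, and 24 h is about eight half-lives at 3 h (24/3 = 8), so a drug-driven QTc maximum there is unlikely. For BA/FE, protocol 7.3.4 plans only that relevant ECG findings be reported as AEs, so the BA/FE categories go beyond the protocol. These points lower the stakes but do not remove the inconsistency: protocol 7.3.4 applies the REP to ECGs, the SAP adopts 36 h for both parts, and SAP 5.3.1 does use Table 6.7:5. A reader might infer that the 24 h ECG is lost altogether. It is not: listings and by-time descriptive statistics keep it, and SAP 6.1 removes only follow-up laboratory values from summaries.

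**On repeats.** A reader might infer that the SAP knowingly analyses the faulty tracing. No text says so. An unreadable tracing may drop out as missing, the central laboratory applies lead fallback and cardiologist review in the 30 mg group, and SAP sections 10.1 to 10.3, which are not in the public text, may define a repeat. A reader might also infer that stopping decisions suffer, because the QTc rule requires a finding "as confirmed by a repeat ECG recording". They do not: on-study cardiac safety uses the QT and QTcF values read at the site, not the SAP analysis set.

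**On the cap of three.** SAP 7.8.4 also drops "More than 3 single ECGs (i.e., measurements from 4th single ECG onwards will not be included)" and does not name the unit. A reader might infer that a nine-tracing baseline shrinks to three. SAP 6.7 rules this out: "Three triplicate ECGs will be recorded as the baseline before the first drug administration within each treatment period", and the baseline is the mean over all three triplicates, which cannot be formed if the later tracings are removed. In the 30 mg group only three baseline tracings are transferred by design, so the cap has no effect there.

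**On unscheduled ECGs.** Their exclusion from interval analysis is stated in both protocol and SAP. Preferring another rule is not grounds for calling this an error.

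**Conclusion.** Two corrections stand.

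The BA/FE 24:00 label is wrong against the SAP's own 36 h window, protocol 7.3.4 and the SRD table. It removes 1 of 6 ECG times per period, 16.7% of planned BA/FE subject-time points within 36 h, from the on-treatment QT and QTcF categories. This figure assumes 12 subjects completing three periods. It also assumes that the follow-up label begins at the 24:00 row, as it does in the public text, where merged cells are flattened.

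The repeat rule, read literally, discards valid replacement tracings that the protocol assigns to the scheduled time point. Its size is unknown, and it is subject to whatever SAP sections 10.1 to 10.3 say.

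The cap of three needs only a wording clarification. The documents do not support a claim of a reduced baseline, of deliberate use of faulty tracings, or of any effect on stopping decisions. All the analyses concerned are descriptive safety analyses; no primary endpoint changes.

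**What to change.** 1. In SAP Table 6.7:5, label the BA/FE 24:00 ECG as on-treatment, so that follow-up starts at 48:00 as in Table 6.7:4.
2. In SAP 7.8.4, replace the blanket exclusion of repeats with a rule that an ECG repeated for quality is analysed in place of the tracing it replaces, at that scheduled time point. Check SAP sections 10.1 to 10.3 first for an existing definition.
3. Add the words *per triplicate* to the rule on the fourth and later single ECGs, and apply it after the substitution in step 2. Otherwise a repeat within a triplicate could itself be dropped as the fourth tracing.

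The cost is SAP wording and programming flags. No new measurements are needed. Step 2 assumes that the repeat tracings and the reason for each repeat can be identified in the database, which should be confirmed.
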